2.3 Study Rationale

While motor deficits in the non-paretic arm of patients with unilateral stroke have been documented as early as 1967 [42], more recent research has shown that these deficits are functionally limiting and that they persist throughout the chronic phase of stroke [6-9, 11, 17, 19-22, 29, 31, 33, 43-51]. In fact, studies of non-paretic arm function in chronic stroke patients have reported performance deficiencies on a number of clinical tests, including the Purdue Pegboard Test [52], the Jebsen-Taylor Hand Function Test [8], and a variety of tests that directly assess or simulate activities of daily living [11, 53, 54]. Furthermore, significant deficits in movement coordination and accuracy have been shown through studies that use motion analysis [7-9, 17, 28-30, 33, 43, 46, 48, 55-62]. [name]'s laboratory published some of the earliest research characterizing the hemisphere specificity of ipsilesional movement deficits in stroke [50, 59] while in the previous grant cycle, [name] systematically detailed the hemisphere specificity, neural foundations, and functional implications of non-paretic arm motor deficits [9, 17, 28-30, 32, 33, 43, 60]. Together, our findings have demonstrated that stroke-related non-paretic arm motor deficits result from a loss of the contributions of the ipsilateral hemisphere to motor control, and that right- and left-hemisphere damage lead to deficits in different aspects of motor control [9, 29, 36, 59, 63]. Most relevant to the current proposal is the finding that hemisphere specific motor deficits in the non-paretic arm produce deficits in functional performance [8]. Our findings have demonstrated that stroke-related non-paretic arm motor deficits result from a loss of the contributions of the ipsilateral hemisphere to motor control, and that right- and left-hemisphere damage lead to deficits in different aspects of motor control [9, 29, 36, 59, 63]. Most relevant to the current proposal is the finding that hemisphere specific motor deficits in the non-paretic arm produce deficits in functional performance.

3.0 Inclusion and Exclusion Criteria

3.1 Inclusion Criteria

1. Right handed (pre-stroke)
2. Neurological confirmation of unilateral stroke
3. Ipsilesional deficits (JTHFT > 70 seconds or 40 (RHD)/45 seconds (LHD) seconds without writing time), contralesional deficits (upper extremity) (UEFM mass extension and prehension components score of 0)
4. Over the age of 18
5. Chronic stage of stroke

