Aim 1: To determine whether non-paretic arm VRMT in chronic stroke survivors with severe paresis will produce durable improvements in non-paretic arm motor performance that will generalize to improve functional activities and functional independence to a greater extent than conventional therapy focused on the paretic arm. We predict that: 1a) Unilateral VRMT training of the non-paretic arm will produce functional improvements in non-paretic arm motor performance (JTHFT), 1b) Conventional therapy focused on the paretic arm should decrease paretic arm impairment (Fugl-Meyer) to a greater or equal extent than non-paretic arm VRMT. We will assess paretic arm impairment level using the upper extremity component of the Fugl-Meyer Assessment (UEFM) as our primary measure, and "work area" using kinematic analysis, as detailed by Dewald and Co-workers [5] as our secondary measure. 1c) The effects of non-paretic arm VRMT will generalize to functional activities (Abilhand) and functional independence (FIM-motor/Barthel) to a greater extent than conventional paretic arm therapy. This aim provides a strong test of our hypothesis that non-paretic arm motor training will have a greater impact on functional independence than conventional paretic arm training in patients who lack paretic hand function, a prediction supported by our pilot data (see Figure 8).

Aim 2: To determine whether intervention-induced improvements in non-paretic arm performance are associated with improvements in hemisphere-specific reaching kinematics. We predict that VRMT-induced improvements in performance will be correlated with reductions in hemisphere-specific motor deficits [6-9], which are targeted by the VR component of our intervention. We will test this using a planar reaching paradigm that we developed and employed in the previous cycle of this grant for

quantifying hemisphere-specific non-paretic arm kinematics [6]. We predict that improvements in functional performance (JTHFT) will correlate better with *early trajectory variance* in LHD patients, but with *late trajectory variance* in RHD patients. These variables have previously been associated with left and right hemisphere processes, respectively.

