2.0 Background

2.1 Scientific Background and Gaps

Stroke is a major health problem in the United States that leaves many survivors with chronic motor impairment, including hemiparesis in the limbs that are on the opposite side of the body to the damaged brain hemisphere. A substantial body of research has now established that the non-paretic arm often has motor deficits that limit performance of activities of daily living and thus functional independence [6, 8, 11-22]. The significance of the proposed research is that we developed a targeted remediation protocol to ameliorate persistent functional performance deficits in chronic stroke patients with severe paresis, who's non-paretic arm impairments are generally ignored in most current rehabilitation protocols. Our intervention protocol is grounded in the premise that targeted remediation of fundamental control deficits exhibited by the non-paretic arm will generalize and transfer beyond practiced tasks to functional activities and functional independence. The previous cycle of this grant detailed the mechanistic underpinnings of non-paretic arm motor deficits. The scientific premise of this proposal is based on the finding that non-paretic arm motor deficits become functionally limiting in patients with severe paresis, who are unable to use the paretic arm for manipulation [23]. This group of patients is identified by an upper extremity Fugl-Meyer (FM) score between 0-28 and a score of 0 (inability to perform) in the mass extension and prehension components of the Fugl-Meyer Assessment.

Woytowicz et al [1] recently reported a cluster analysis of 247 stroke patients, and identified a severely paretic group in the FM score range of 0-28. With the exception of mass finger flexion, 95-100%

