of the patients scored 0 (unable to perform) for each item of the wrist movement, mass finger extension, and each prehension item of the FM. Thus, this severely paretic group of stroke patients is unable to use the paretic arm for manipulation purposes in activities of daily living. Deficits in coordination of the non-paretic arm can thus produce substantial limitations in the speed and efficacy of functional activities in this population. In fact, our preliminary findings (see Figure 2) indicate that unilateral tasks with the non-paretic arm take, on average, twice as long to complete as the comparable arm of age-matched control participants, indicating labored and inefficient movement that can interfere with patient's participation in activities. Unfortunately, clinical rehabilitation has yet to recognize the need to address non-paretic arm motor deficits, largely because scientific evidence has not yet been translated into clinical practice, nor has the best practice for this translation been specified through innovative intervention studies. This proposal will directly address these shortcomings, in order to provide a model for understanding how to incorporate non-paretic arm motor training into clinical rehabilitation practice for patients with severe paresis. It should be noted, however, that in animal models, training of the non-paretic arm in the acute phase of stroke recovery has been shown to interfere with subsequent paretic arm recovery [24, 25]. In addition, constraining the use of the non-paretic arm can facilitate functional recovery in those stroke survivors with mild to moderate paresis who are capable of distal manipulation in the contralesional hand, but who avoid using that arm due to learned non-use [26, 27].

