tasks that simulate the coordination requirements of functional daily activities [66, 67]. The left column in Figure 2 (control) shows the difference between healthy participants performing with the non-dominant left arm (Black) and the dominant right arm (Grey). The data are stratified on the x-axis by hand, and severity of contralesional paresis, as measured by the upper extremity component of the Fugl-Meyer Assessment of motor impairment [68] (mild [43-66], moderate [29-42], Severe [0-28]). In stroke survivors, JTHFT scores are only for the non-paretic arm (ie. Gray = non-paretic right arm of RHD participants; Black = non-paretic left arm of LHD participants). Note that the 'severe' classification in this plot reflects the level of impairment we target in this proposal.

In stroke survivors, JTHFT performance with the non-paretic arm was impacted substantially by both the severity of paresis and the side of brain damage. Participants with the most severe paresis in the contralesional arm had the greatest motor deficit in the non-paretic arm. Furthermore, the magnitude of the deficit depended on the side of the lesion, such that left hemisphere damage was associated with a 115% increase in JTFT score, while right hemisphere damage increased the time to complete the JTFT by 66%. These comparisons are relative to performance of the same arm (right or left) of age-matched control participants. However, it should be stressed that in LHD patients, the non-dominant arm must now function as a dominant controller, indicating an even larger deficit relative to age-matched dominant arm performance. Thus, stroke survivors who are forced to rely most extensively on the non-paretic arm for performance of ADL have the greatest deficits in coordination in the non-paretic arm. These stroke survivors were tested, on average, 1.8 years (± 0.3 SE) after stroke, which suggests that these deficits do not spontaneously improve over time. To provide a reference, imagine using only your non-dominant arm to carry out all your activities of daily living, such as preparing food, dressing including buttoning, putting on socks, and shoes, etc. This would be somewhat frustrating. Now imagine that your non-dominant arm has become 115% slower and less coordinated than it was—the case for our severely impaired LHD patients. RHD patients get to use the previously dominant arm, but with a 66% decrement in function. Overall, these impairments are substantially functionally limiting.

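### Inclusion criterion 3 omits the UEFM 0-28 limit that Sections 2.1 and 2.2 use to define severe paresis, so some patients with totals above 28 can be enrolled

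*Combined protocol and SAP*

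**What the plan says.** Section 2.1 (Scientific Background and Gaps) says the target group is "identified by an upper extremity Fugl-Meyer (FM) score between 0-28 and a score of 0" on the mass extension and prehension components. The two conditions are joined, so both must hold.

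Section 2.2 (Previous Data) sets out bands on the UEFM total: "mild [43-66], moderate [29-42], Severe [0-28". It adds that the severe "classification in this plot reflects the level of impairment we target in this proposal". Aim 1 in Section 1.1 concerns "non-paretic arm VRMT in chronic stroke survivors with severe paresis".

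In Section 3.1, the paretic-arm part of inclusion criterion 3 reads "contralesional deficits (upper extremity) (UEFM mass extension and prehension components score of 0". It sets no limit on the UEFM total. The same criterion also requires a non-paretic-arm deficit: JTHFT above 70 seconds, or above 40 seconds (right-hemisphere damage) or 45 seconds (left-hemisphere damage) without writing time. The other inclusion criteria cover handedness, unilateral stroke, age and chronicity. The exclusions in Section 3.2 do not mention the UEFM.

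**The concern.** Section 3.1 is the text the two sites apply when deciding who enters. It contains one of the two conditions that define the population in Section 2.1. Unless zero hand items by themselves guarantee a total of 28 or less, the trial can enrol patients whom the protocol's own bands class as moderate.

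What is at stake is the population to which the result applies. The aims, background and rationale are all written for severe paresis. Section 8.3 names no severity stratum or subgroup analysis that would recover an answer for the 0-28 group alone. One site could also screen by Section 2.1 and the other by Section 3.1, which would give the sites different populations.

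**Working it through.** The plan states no figure for this point, so the check compares the texts and then makes one short calculation.

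**1. The conditions side by side**

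| Place | UEFM total 0-28 | Mass extension and prehension = 0 |
|---|---|---|
| 2.1, definition of the group | required | required |
| 2.2, level targeted | severe band, 0-28 | not mentioned |
| 3.1, criterion 3 | absent | required |
| 3.1, other criteria, and 3.2 | absent | absent |

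**2. Does the cited cluster analysis close the gap?** Section 2.1 reports that, within the 0-28 group, 95-100% "of the patients scored 0 (unable to perform) for each item of the wrist movement", and likewise for mass finger extension and each prehension item. That is the proportion with a zero item score given a severe total. Closing the gap needs the reverse: the proportion with a severe total given zero hand items. The documents do not give it, and it cannot be derived without the item scores of patients above 28.

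**3. Can a patient with zero hand items score above 28?** The top of the scale is 66 (Section 2.2). The documents do not give the item structure, so I assume 0-2 points per item. If *k* items are zeroed, the highest possible total is

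maximum total = 66 − 2*k*

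| Items zeroed, *k* | Highest possible total |
|---|---|
| 2 | 62 |
| 6 | 54 |
| 10 | 46 |
| 18 | 30 |
| 19 | 28 |

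Zero hand items force a total of 28 or less only if 66 − 2*k* ≤ 28, that is *k* ≥ 19. On the same assumption the scale has 66 / 2 = 33 items, so criterion 3 would have to zero more than half of them. It names only mass extension and prehension. It does not require zeros on the wrist items or on mass flexion. Totals of 29-42 are therefore attainable under Section 3.1 for any plausible *k*.

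This shows that such totals are possible, not how common they are. Section 7.1 describes the typical participant as having partial shoulder abduction and partial elbow extension. Some proximal points are therefore expected, but the section does not say how many.

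**The case against.** The strongest reply is that criterion 3 keeps the condition that carries the rationale. Sections 1.1 and 2.1 argue that non-paretic-arm deficits become limiting when the paretic hand cannot be used for manipulation. A patient at 29-42 with zero mass extension and prehension still fits that description. Criterion 3 also requires a measured JTHFT deficit, so everyone enrolled has the impairment that the training targets. Both points stand, and they limit the consequence. They do not restore the 0-28 condition, which Section 2.1 states in addition to the hand items.

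A second reply is that internal validity is intact: patients are randomised, the UEFM is measured at baseline, and the mixed models in Section 8.3 allow covariates. That also stands. The point concerns who the result describes, not bias between the arms.

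Three stronger readings are tempting, and the documents do not support them.

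- A reader might infer that patients above 28 have less to gain from the experimental training, because Section 2.2 shows deficits rising with severity. Those data are not described as restricted to patients who pass the JTHFT threshold, so the gradient cannot be carried over to patients who do.
- A reader might infer that these patients would gain more from the paretic-arm comparator. Nothing in the documents relates comparator benefit to the UEFM total.
- A reader might infer a material loss of power. That needs the share above 28 and their relative gain, and neither is given. As illustration only, suppose 10-30% are above 28 and gain half as much. The effect is multiplied by 1 − 0.10 × 0.5 = 0.95 down to 1 − 0.30 × 0.5 = 0.85. With *f* = 0.35 (*d* = 0.70), an assumed two-sided alpha of 0.05 and 60 per group, power in a two-group t test falls from 0.967 to 0.951-0.898, still above the planned 0.80. With 40 per group (20 completers a year in Section 8.1 over the four years in Section 16.2, giving 80), it falls from 0.871 to 0.836-0.748. The number of completers is a separate question, and the dilution inputs have no basis in the documents.

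The telephone screening script mentioned in Section 4.4 is not in the documents and might contain the limit. Even if it does, the protocol's eligibility criteria should state it.

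**Conclusion.** The inconsistency is real. Sections 2.1 and 2.2 define and target a UEFM total of 0-28, Section 3.1 omits that limit, and nothing else in the eligibility criteria supplies it. Followed as written, Section 3.1 can admit patients in the moderate band provided they score zero on mass extension and prehension and meet the JTHFT threshold. That these patients can reach 29-42 rests on the assumed 0-2 points per item.

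The effect is a mismatch between the population that can be enrolled and the severe-paresis population in the aims. Its size cannot be computed from the documents. A reader might conclude that moderately paretic patients in general can enter, or that the trial no longer addresses severe paresis. Neither follows: entry above 28 is confined to patients without these hand functions, and patients at 0-28 who meet the criteria remain eligible.

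**What to change.** Reconcile Section 3.1 with Sections 2.1 and 2.2. The direct change is to add a UEFM total of 0-28 at screening to criterion 3, required jointly with the zero scores on mass extension and prehension. The UEFM is a primary measure already scored at Visit 1 before randomisation (Section 7.2.1), so no new procedure or visit is needed. The cost is an edit to the eligibility wording and a slightly smaller eligible pool.

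If the wider population is intended, leave criterion 3 as it is. Reword the aims in Section 1.1 and the population definition in Sections 2.1 and 2.2 to match it.

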3.2 Exclusion Criteria

1. Neuroradiological confirmation of extensive periventricular white matter changes (based on consultation with neuroradiology)

A history of:

- 1) neurological disease other than stroke (e.g., head trauma),
- 2) a major psychiatric diagnosis (e.g., schizophrenia, major affective disorder),
- 3) hospital admission for substance abuse
- 4) peripheral disorders affecting sensation or movement of the arms, including pain or arthritis
- 5) currently taking prescription drugs with known sedative properties that might interfere with sensory-motor function
- 6) significant joint pain that is activity limiting.

3.3 Early Withdrawal of Subjects

3.3.1 Criteria for removal from study

- failure of subject to adhere to protocol requirements (attending sessions)
- subject consent withdrawal
- new stroke or disabling disorder

3.3.2 Follow-up for withdrawn subjects

Following withdraw from the study investigators will call participants 1 week later to follow up. Data will be used if enough has been collected for analysis. If not, subject will be replaced by additional recruitment.

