7.2 Study Procedures

7.2.1 Visit 1 (pre-test 1):

Visit 1 (pre-test/screening): subjects will be consented, and then tested using standardized tests including the primary and secondary measures. In addition, the Edinburgh handedness inventory, Confidence in Arm and Hand Movement (CAHM), Multidimensional Scale of Perceived Social Support, NIH stroke scale, tests for comorbidities including testing of grip strength, visual neglect, and apraxia. If they meet criteria for the study, they will be randomly assigned to either the intervention or comparison condition. Tests may be videotaped for scoring and standardization purposes. Participant's names will not be associated with the videotapes. A data safety monitoring board will monitor the study for safety and to minimize risk.

7.2.2 Visit 2 (pre-test 2):

Visit 2 will include the same assessments as visit 1 to establish stability in baseline measures. Participants will also receive an MRI of the brain, which will take about one hour, as long as they are able to have one. The research grade MRI is used for data analysis regarding lesion location and volume. It is standard for studies of this nature to collect this information.

7.2.3 Visit 3-17:

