7.2.4 Visit 18: Post test

Visit will include the same assessments as visit 1

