7.2.6 Visit 20: Post test 3 (long term retention)

Visits will include the same assessments as visit 1 six months following completion of training sessions

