8.3 Statistical methods

To assess our intervention, we will fit linear mixed models (LMMs) with single-degree-of-freedom linear contrasts [80] to determine if the data support our predictions (see next section). We will use a linear mixed model with main effects for group (experimental, control) and time (Test) and the group by time interaction simply provides a more flexible approach to the typical analysis of variance (ANOVA) model for a randomized pretest-posttest design. Specifically, LMMs will permit us to account for participant matching with a random cluster effect; and they permit each participant to have her or his initial value (random intercept) and different change patterns across the tests (random coefficients for an underlying piecewise regression). LMMs allow us to use covariates to adjust for any potential confounders. Finally, these models can tolerate missing data on the response, which is not true of the standard ANOVA-based model.

Lesion Reconstruction Methods: [name]'s laboratory personnel will reconstruct stroke lesions from the research grade MRI scans. They will superimpose lesions on each axial slice to identify common areas of lesion overlap associated with damage to the right or left hemisphere and to assess comparability of intrahemispheric lesion location in our two tracks. This grant will not specifically examine intrahemispheric lesion location, but these data will provide pilot data for future studies. To calculate the CST lesion load, we will use the tractography based atlas of human brain connections from the natbrain lab [72]. We will use the MRICron descriptive tool for the calculation of the CST-lesion overlap volume. The binary lesion mask file will be overlaid onto either the left or right binary template CST atlas, and the percentage of CST which overlaps with the lesion is calculated.

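### People who stop during training have no planned post-test, and Section 3.3.2 lets randomised participants be replaced when their data are not enough, a term the plan does not define

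*Combined protocol and SAP*

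**What the plan says.** All references are to the combined protocol and SAP.

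- **Randomisation** takes place at Visit 1 (7.2.1), before the second pre-test and all training: "If they meet criteria for the study, they will be randomly assigned to either the intervention or comparison condition".
- **Removal from the study** (3.3.1) covers withdrawal of consent, "failure of subject to adhere to protocol requirements (attending sessions") and "new stroke or disabling disorder".
- **After removal** (3.3.2): "Following withdraw from the study investigators will call participants 1 week later to follow up". The rule on use of data follows: "Data will be used if enough has been collected for analysis. If not, subject will be replaced by additional recruitment". No threshold, number of visits, decision-maker or timing is given.
- **Outcome tests after baseline** are at Visits 18, 19 and 20, once training (Visits 3 to 17) is over. For Visit 18: "Visit will include the same assessments as visit 1". Visits 19 and 20 are timed from the end of training; for the last: "Visits will include the same assessments as visit 1 six months following completion of training sessions".
- **Analysis** (8.3) is by linear mixed models (LMMs), chosen partly because "these models can tolerate missing data on the response". No analysis set is named in the text available.
- **Drop-outs** are reported to the investigators and retention is monitored (18.4), but that section plans no outcome collection.

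**The concern.** There are two separate gaps, and the first is the larger.

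1. A participant removed between Visits 3 and 17 has baseline scores only, and nothing says that person is seen again for outcome testing. The arms ask for different work: VR and dexterity training of the non-paretic arm, or assisted reaching with a severely paretic arm. Loss may therefore differ by arm and be related to progress. If so, the Aim 1 contrasts compare groups that are no longer the randomised ones. Recruiting replacements restores the numbers but not the comparability.
2. For a participant who leaves after Visit 18, the meaning of *enough* matters in itself. If it means usable by the LMM, the Visit 18 score stays in. If it means complete post-tests, the person is left out and replaced, although the model does not need that. The six-month contrast, which bears on the durability claim in Aim 1, is the one exposed.

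**Working it through.** **The plan's own figure, for scale.** Section 8.2 claims power of at least 0.80 with 60 per group at Cohen's f = 0.35. The plan does not state d; for a simple two-group comparison d = 2f = 0.70. Alpha is not stated either; take two-sided 0.05. Power = Φ(0.70 × √(60/2) − 1.96) = Φ(3.834 − 1.960) = Φ(1.874) = 0.970, so the bound is met. The same target needs 2 × (1.960 + 0.842)² / 0.70² = 32.04, so 33 per arm. The issue is therefore bias more than power.

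**Inputs.** The only loss figure is in 8.1: 30 recruited and 20 completing per year, which combines screening with attrition. Loss after randomisation is unknown, so everything below is assumed:

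- no true effect, 60 analysed per arm, analysis adjusted for baseline;
- pre-post correlation ρ = 0.5 to 0.7;
- correlation r = 0.3 to 0.5 between the tendency to stay and the outcome;
- loss by arm of 10% vs 5%, 20% vs 10%, and 33% vs 10%. The last is extreme, because the one third in 8.1 includes screening failures.

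**Step 1: stopping during training, no post-test.** If the fraction p with the lowest tendency to stay is lost, the mean tendency among those left is λ(p) = φ(z_p)/(1 − p). This gives λ(0.05) = 0.109, λ(0.10) = 0.195, λ(0.20) = 0.350 and λ(0.33) = 0.541. The baseline-adjusted bias is

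r × (1 − ρ²) × [λ(p₁) − λ(p₂)].

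The multiplier runs from 0.3 × (1 − 0.49) = 0.153 to 0.5 × (1 − 0.25) = 0.375. The standard error is √[(2/60)(1 − ρ²)], which is 0.130 at ρ = 0.7 and 0.158 at ρ = 0.5.

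| Loss by arm | Difference in λ | Bias (SD) | Two-sided 5% error |
|---|---|---|---|
| 10% vs 5% | 0.086 | 0.013–0.032 | 5.1–5.5% |
| 20% vs 10% | 0.155 | 0.024–0.058 | 5.4–6.6% |
| 33% vs 10% | 0.346 | 0.053–0.130 | 6.9–13% |
| 20% vs 20% | 0 | 0 | 5% |

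Simulation of whole trials gave the same ranges to within about 0.005 SD.

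**Step 2: does keeping baseline scores in the LMM help?** No. In simulated trials, retaining baseline-only participants gave 0.015–0.031, 0.023–0.062 and 0.053–0.128 SD. Excluding and replacing them in the same trials gave 0.015–0.030, 0.024–0.061 and 0.054–0.130 SD. A baseline score says nothing about the part of the outcome that baseline does not predict.

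**Step 3: what do recovered post-tests do?** If a random share q of those lost is assessed, λ becomes (1 − q)φ(z_p)/[1 − p(1 − q)]. At q = 0.5 the bias falls to 0.006–0.015, 0.010–0.024 and 0.019–0.047 SD. Random recovery is the favourable case.

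**Step 4: leaving after Visit 18, six-month contrast.** Assume a Visit 18 to Visit 20 correlation of 0.8 to 0.9. These are simulated bias ranges in SD.

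| Dropout depends on | Handling | 10% vs 5% | 20% vs 10% | 33% vs 10% |
|---|---|---|---|---|
| Visit 18 score | excluded and replaced | 0.01–0.03 | 0.01–0.06 | 0.03–0.12 |
| Visit 18 score | kept in LMM | about 0 | about 0 | about 0 |
| unseen Visit 20 score | excluded and replaced | 0.01–0.03 | 0.02–0.06 | 0.05–0.14 |
| unseen Visit 20 score | kept in LMM | 0.00–0.02 | 0.01–0.03 | 0.02–0.07 |

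For this group, unlike the group in Step 2, the reading of *enough* changes the answer.

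**The case against.** The best defence reads 3.3.2 together with 8.3. The only analysis described is an LMM that accepts missing responses, so a participant with a Visit 18 score has enough, and replacement may mean no more than topping up numbers. That reading is plausible, and under it few or none are excluded. It answers the second gap if adopted, but the text does not adopt it. It does not touch the first gap, since a model cannot supply post-tests that nobody planned to collect.

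Two further objections stand in part. Recovery will be incomplete: people who withdraw consent to follow-up cannot be assessed, non-attenders may not return, and results after a new stroke are hard to interpret. Also, Sections 8.2 and 8.3 point to further analysis text and 18.4 to an uploaded grant. None of these was available, so an analysis set may be defined there.

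A reader might infer three stronger things. One is that the undefined *enough* is itself the main source of bias; Step 2 shows that it makes no difference for people lost during training. Another is that the plan drops everyone with incomplete data; it permits that reading but does not require it. The third is that a third of those randomised will be lost; the figures in 8.1 mix screening with attrition and cannot show this.

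**Conclusion.** The point holds in a limited form. Followed as written, the plan collects no post-test from anyone removed during training and allows a randomised participant to be replaced on a judgement made after randomisation. The missing post-tests are the main source of possible bias. The ambiguity over *enough* is a separate, lesser matter that affects only those who leave after Visit 18.

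On the assumptions above, bias is about 0.01 to 0.06 SD for loss of 10% vs 5% up to 20% vs 10%, and near zero if loss is equal and equally informative across arms. Values up to about 0.13 SD need an extreme imbalance. The milder values are small beside d = 0.70, which is itself a conversion of the f in 8.2. No loss rate, recovery rate or correlation comes from the documents, so the actual bias cannot be derived. The wording of 3.3.2 is certain; the absence of an analysis set is certain only for the text available. This is a cheap improvement that should be made, and it does not by itself invalidate the design.

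**What to change.** Replace the last two sentences of 3.3.2 with:

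> Participants who stop training are invited to the Visit 18, 19 and 20 assessments, at target dates counted from randomisation that match the planned schedule for completers, unless they withdraw consent to follow-up. All randomised participants are analysed in their assigned group using every available measurement in the LMM. Additional recruits are newly randomised and displace no randomised participant.

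Dates need to be counted from randomisation because the present schedule has no anchor for someone who does not finish training.

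In 8.3:

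- add a missing-not-at-random sensitivity analysis that shifts the missing post-tests in one arm by increasing amounts and reports the shift at which the conclusion changes;
- state how outcomes measured after a new stroke or disabling disorder are handled;
- commit to reporting the numbers randomised, withdrawn and assessed by arm at each of Visits 18 to 20;
- if an analysis set is defined in another document, cite it and align 3.3.2 with it.

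Reconcile the non-attendance ground for removal in 3.3.1 with the make-up provision for missed sessions in 7.3.

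**Cost.** Section 14.0 pays $50 per visit plus up to $50 travel. Three visits therefore cost 3 × $50 = $150 to 3 × $100 = $300 per withdrawn participant. That is $1,800 to $3,600 if 12 of 120 withdraw, and $3,600 to $7,200 if 24 do, plus assessor time. Including people who stopped training may slightly dilute the effect estimate. Additional recruitment remains allowed, so planned power need not fall.
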